**Table 9.1.1: Schedule of Events – Screening and Infusion**

Assessment	Prior to BMN 270 Infusion			BMN 270 Infusion Visit (Day 1) k
	Screening* (Day -28 to Day -1)	Smart Rescreening i (Day -28 to Day -1)	Baseline (Day -7 to Day -1) h	
Informed consent	X			
Demographics (age, sex, race, ethnicity)	X			
Medical History	X			
Physical Examination a	X		X	X
Height and Weight	X			
Vital Signs	X	X	X	X
Assessment of Adverse Events and Concomitant Medications	X	X	X	X
Documentation of bleeding episodes and FVIII usage for previous 12 months (by either subject or clinical information)	X	X	X	
Distribution of subject diaries and training in their use l	X			
Electrocardiogram	X			
Liver Ultrasound	X			
hFVIII Assays b	X	X j	X	
AAV5 TAb Assays c	X	X	X	X
AAV5 TI Assay			X	
Screen for Hepatitis B, Hepatitis C, HIV d	X			
Blood chemistry, hematology, and coagulation tests e	X	X	X	
Fasting lipid panel (blood triglycerides, total cholesterol, HDL cholesterol, and LDL cholesterol)				X
Urine Tests e	X	X	X	
Liver Tests e	X	X	X	
PBMC collection (for baseline determination of AAV5 and FVIII specific cellular immunity)			X	

Assessment	Prior to BMN 270 Infusion			BMN 270 Infusion Visit (Day 1) k
	Screening* (Day -28 to Day -1)	Smart Rescreening i (Day -28 to Day -1)	Baseline (Day -7 to Day -1) h	
Von Willebrand Factor Antigen (VWF:Ag)			X	
TGA Assay g			X	
PCR of vector DNA in blood, saliva, urine, semen, and stools			X	X
Biomarker testing f	X			
Exploratory biomarker assessments g			X	X
Haemo-QOL-A assessment			X	
EQ-5D-5L			X	
HAL			X	
WPAI+CIQ:HS			X	
PROBE			X	
BMN 270 Infusion				X
Hypersensitivity blood assessments m				X m

\* Screening assessments should be performed within 28 days of BMN 270 infusion (and must be performed within 42 days prior to BMN 270 infusion).

a Complete physical examination should be done at Screening. Brief physical examination may be done at Baseline and at the BMN 270 Infusion Visit.

b Includes baseline FVIII activity (chromogenic substrate FVIII assay and one-stage clotting FVIII assay), coagulation exploratory assay, hFVIII inhibitor level (Bethesda assay with Nijmegen modification), hFVIII total antibody titer, and hFVIII protein assay. Baseline activity should be assessed at trough (at least >72 hours after last dose of replacement FVIII therapy, or 5x the known half-life of the FVIII concentrates administered).

c Sample collection on the day of the infusion visit must be performed before the BMN 270 infusion is given. Screening, Smart Re-screening, and Infusion Day samples will be tested in an AAV5 TAb pre-screening assay specifically developed for enrollment purposes. Baseline and all post-dose samples will be tested in a different AAV5 TAb post-dose immunogenicity monitoring assay

d Patients with documented negative results within the last 30 days do not need to be retested. Hepatitis B screening should include hepatitis B surface antigen (HBsAg), hepatitis B surface antibody (HBsAb), and hepatitis B core antibody (HBcAb).

e Refer to [Table 9.7.8.2.1](#) for laboratory assessments to be included, and to [Table 9.7.8.3.1](#) for liver tests. ABO blood typing assessment should be performed as part of the hematology assessment (at Baseline, or at another regularly scheduled visit prior to the end of the subject's participation in the study).

f Includes HLA genotyping and FVIII genotyping.

g Blood samples will be collected from subjects to evaluate biochemical, molecular, cellular, and genetic/genomic aspects relevant to hemophilia A, coagulation, and/or AAV gene transfer, and to develop assays used for these evaluations. Subjects may choose to opt out of the exploratory genetic/genomic research being done to study or try to discover genes that are not yet known to be associated with hemophilia A. While exploratory samples will be collected at the time points indicated above, testing of these samples (including those for TGA assay, and any other exploratory assessments) will be performed only as deemed necessary by the Sponsor.

h Should the screening visit occur within 30 days of the drug infusion, physical examination, blood chemistry, LTs, hematology, urine tests, and coagulation tests do not need to be repeated at Baseline.

i Smart rescreening should only be performed if a patient has been determined to be eligible for the study and is unable to complete the Baseline assessments and Infusion prior to the closing of the original Screening window. Subjects who undergo smart rescreening must complete the rescreening assessments and receive the infusion within 90 days of signing the original consent. Subjects who do not complete dosing within 90 days will be required to re-consent and undergo all screening procedures. Subjects may not undergo smart rescreening more than once.

j Only the hFVIII inhibitor level (Bethesda assay with Nijmegen modification) assay must be done at smart rescreening.

k With the exception of the collection of samples for PCR vector DNA analysis, assessments on the day of infusion must be performed prior to the infusion. Subjects will fast for at least 8 hours prior to pre-infusion laboratory sampling on the day of the infusion visit. On the day of the BMN 270 Infusion, vital signs will be monitored prior to the infusion, during the infusion every 15 minutes ( $\pm$  5 minutes), and following the infusion hourly ( $\pm$  5 minutes) for at least 8 hours during the subject's stay in the clinic. Shedding samples for PCR of vector DNA (blood, saliva, urine, semen, stool) should be collected between 2 and 24 hours after the infusion has been completed.

l Diaries should be distributed to subjects who have consented to participate in the study and who have been determined to meet all study eligibility criteria.

m In case of hypersensitivity or adverse drug reaction, safety assessment, including physical examination and vital signs, will be done and additional blood samples will be collected [REDACTED]

[REDACTED] In-patient observation can be extended and additional blood samples can be collected if deemed necessary at the discretion of the Investigator and Medical Monitor.

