**Table 9.1.2: Schedule of Events – Post-Infusion Follow-Up (Week 1-16)**

Assessment	Follow-Up After BMN 270 Infusion – Weeks*																
	Week 1		2	3	4	5 g	6	7 g	8	9 g	10	11 g	12	13 g	14	15 g	16
	D4	D8															
Study Day*	4	8	15	22	29	36	43	50	57	64	71	78	85	92	99	106	113
Physical examination a		X	X	X	X	X g	X	X g	X	X g	X						
Weight a					X				X				X				X
Assessment of Adverse Events and Concomitant Medications (including review of subject diary for bleeding and FVIII use)		X	X	X	X	X	X	X	X	X	X	X	X	X	X	X	X
Vital Signs		X	X	X	X	X g	X	X g	X	X g	X						
Blood chemistry, hematology, and coagulation tests b			X		X						X						X
Urine Tests b														X			
Liver Tests b	X	X	X	X	X	X	X	X	X	X	X	X	X	X	X	X	X
FVIII assays c		X	X	X	X	X	X	X	X	X	X	X	X	X	X	X	X
FVIII antibody titer					X				X				X				X
PCR of vector DNA in blood, saliva, urine, semen, and stools d	X	X	X	X	X		X		X			X					X
Exploratory biomarker assessments e							X					X					X
Haemo-QOL-A assessment					X							X					
EQ-5D-5L					X							X					
HAL					X							X					

Assessment	Follow-Up After BMN 270 Infusion – Weeks*																
	Week 1		2	3	4	5 g	6	7 g	8	9 g	10	11 g	12	13 g	14	15 g	16
	D4	D8															
Study Day*	4	8	15	22	29	36	43	50	57	64	71	78	85	92	99	106	113
WPAI+CIQ:HS					X								X				
PROBE					X								X				
AAV5 TAb Assay										X							X
AAV5 TI Assay										X							X
Testing for reactivation of hepatitis B and hepatitis C																	X f
PBMC collection (for determination of AAV5 and FVIII specific immunity)			X		X		X		X		X		X		X		X
VWF:Ag													X				

\* Visit windows are  $\pm$  48 hours (and include the Day 4 visit).

a Brief physical examination should be done at all weekly visits.

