## **10.3 Methods and Timing for Capturing and Assessing Safety Parameters**

### **10.3.1 Adverse Event Reporting Period**

The study AE reporting period is as follows:

- After informed consent but prior to initiation of study drug, only SAEs associated with any protocol-imposed interventions will be collected; AEs occurring during this time period should be recorded on the Medical History eCRF.
- After informed consent is obtained and following infusion of study drug, the reporting period for all non-serious AEs and SAEs begins and continues for approximately 5 years or until study discontinuation/termination, whichever is longer.

The criteria for determining, and the reporting of SAEs is provided in Section 10.2.

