### **12.5.2 Week 1 – Day 4**

On Day 4 of Week 1, the following procedures will be performed:

- PCR of vector DNA in blood, saliva, urine, semen, and stools
- Liver Tests (refer to [Table 9.7.8.3.1](#))

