### **12.5.3 Week 1 – Day 8**

On Day 8, the following procedures will be performed, in addition to the weekly assessments required in Section [12.5.1](#):

- PCR of vector DNA in blood, saliva, urine, semen, and stools

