14.1.5 Events of Special Interest (EOSIs)

The following events of special interest, which include EOSI defined in the protocol, will be provided in a data listing for each type of EOSI.

- Transaminitis
 - ALT elevations (AE Preferred term: “Alanine aminotransferase increased”).
 - AEs of liver dysfunction, defined using the MedDRA search strategy high level term (HLT = “Liver function analyses”).
 - Potential Hy’s law cases
 - ALT or AST \geq 3x ULN and serum TBL > 2x ULN
 - Assessments of ALT/AST and TBL must be on the same day

A listing will be provided.

- Infusion related reaction, Hypersensitivity, Anaphylactic or Anaphylactoid reactions
 - Infusion related reactions, defined as AEs occurring during BMN 270 infusion or up to 48 hours post-infusion^a, will be summarized as follows:

- Subjects who receive infusion with initial rate of approximately 4 mL/min
- The rest of the subjects, i.e. subjects who receive infusion with initial rate of 1 mL/min
- All treated subjects
- Systemic hypersensitivity (Hypersensitivity [SMQ] - narrow scope), occurring during BMN 270 infusion or up to 48 hours post-infusion^a.
- Anaphylactic, or anaphylactoid reactions (Anaphylactic reaction [SMQ] – algorithmic), occurring during BMN 270 infusion or up to 48 hours post-infusion^a – listing only.
- Thromboembolic events:
 - Embolic and thrombotic events (SMQ).
 - AEs suggestive of thromboembolic events: for subjects who have FVIII elevation > 150% any time during study, a listing of clinical terms suggestive of thromboembolic events observed from the time point prior to when FVIII was elevated until FVIII falls below 150%. (The AE preferred terms are listed in Appendix 19.2.)
- Development of anti-FVIII neutralizing antibodies as measured by the Nijmegen modified Bethesda assay (Preferred term: "Anti factor VIII antibody positive", reported as EOSI)

^a If the number of hours post-infusion cannot be determined, AEs that start two days after the infusion day are excluded.

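### No adverse-event question is scheduled between discharge on infusion day and Day 8, 3–7 days after the SAP's 48-hour reaction window closes, and the infusion-day timing rule needs reconciling

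*Protocol*

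**What the plan says.** **Infusion day.** Table 9.1.1 lists "Assessment of Adverse Events and Concomitant Medications" in the Day 1 column. That column carries footnote k, under which "assessments on the day of infusion must be performed prior to the infusion"; the only exception named in that sentence is PCR sampling. The same footnote then requires vital signs during the infusion and hourly afterwards. Section 12.4 marks the AAV5 antibody and lipid samples as pre-infusion but gives no time for the adverse-event item. Section 9.4.4 keeps the subject in the clinic for a minimum of 8 hours. Before discharge, it has staff explain how to recognise a delayed hypersensitivity reaction and where to seek help.

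**Reporting period.** Protocol Section 10.3.1: "After informed consent but prior to initiation of study drug, only SAEs associated with any protocol-imposed interventions will be collected". Other pre-dose events go to medical history. All adverse events are reportable once the infusion has been given.

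**First week.** Section 12.5.2 begins "On Day 4 of Week 1, the following procedures will be performed" and lists only vector PCR and liver tests. In Table 9.1.2 the row "Assessment of Adverse Events and Concomitant Medications (including review of subject diary for bleeding and FVIII use" is blank at Day 4 and first marked at Day 8. Section 12.5.3 agrees: "On Day 8, the following procedures will be performed, in addition to the weekly assessments required in Section" 12.5.1, and those weekly assessments include adverse events. Visit windows are plus or minus "48 hours (and include the Day 4 visit".

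**SAP.** Section 14.1.5 has infusion-related reactions "defined as AEs occurring during BMN 270 infusion or up to 48 hours" after it, and applies the same limit to systemic hypersensitivity and to anaphylactic or anaphylactoid reactions. Its footnote a says that when the hours since infusion cannot be determined, events starting two days after the infusion day do not count.

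**The concern.** The SAP's reaction category depends on the time of onset in the first two days, but the schedule does not clearly ask for that information until about a week after dosing. If footnote k is followed to the letter, the Day 1 assessment cannot record a reaction to an infusion that has not yet been given. The next scheduled visit, Day 4, takes samples and asks nothing about adverse events.

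Two things are at stake. The first is data quality: a mild or delayed event has to be recalled on Day 8 with a date, and sometimes an hour, that decides whether it enters the 48-hour category. The second is site awareness. The examination and blood samples for a reaction start only once it is recognised, and the 24-hour reporting clock for events of special interest (Section 10.2.1) starts when the site learns of the event. The subject diary is for bleeding and FVIII use, so it does not fill the gap. Section 10.3.2 itself prefers verbal questioning for eliciting adverse events.

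**Working it through.** The plan states no figure for this interval, so there is none to reproduce. The check is a comparison of schedules plus day arithmetic.

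**Inputs**
- Infusion date = Day 1; later study day = date − infusion date + 1 (SAP 5.3).
- Reaction window: up to 48 h after infusion (SAP 14.1.5).
- Visit window: ±48 h, that is ±2 days, including Day 4 (Table 9.1.2).
- Observation: at least 8 h after infusion (Section 9.4.4).

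**Timing**
- Window closes: Day 1 + 2 days = Day 3.
- First scheduled questioning after discharge: Day 8 ± 2 = Days 6–10.
- Delay after closure: 6 − 3 = 3 to 10 − 3 = 7 days; nominally 8 − 3 = 5 days.
- Day 4 visit: Days 2–6, that is 2 − 3 = −1 to 6 − 3 = +3 days relative to closure; nominally 4 − 3 = 1 day after.

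**Hours without scheduled contact**
- 48 − 8 = 40 h; 40/48 = 83%. The 8 h is a minimum and can be extended, so this is an upper bound: up to 40 h.

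**When the onset hour decides the classification**
- Day 1 or Day 2 onset: the end of Day 2 is never more than 48 h after an infusion given on Day 1, so the date alone suffices.
- Day 4 or later: always outside the window.
- Day 3 onset: inside or outside depending on the hour; excluded under footnote a when the hour is unknown.

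So the hour matters on one calendar day. The documents do not give the clock time at which infusions end, so its share of the window rests on an assumption:

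| Assumed end of infusion | Window hours on Day 3 | Share of 48 h |
|---|---|---|
| 10:00 | 10 | 10/48 = 21% |
| 12:00 | 12 | 12/48 = 25% |
| 16:00 | 16 | 16/48 = 33% |

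**Two readings of the Day 1 item**

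| | Footnote k taken literally | Section 12.4 taken broadly |
|---|---|---|
| Day 1 assessment | Before infusion only | May also be after infusion |
| Day 4 | No adverse-event item | No adverse-event item |
| First scheduled questioning after discharge | Day 8 | Day 8 |

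The reading changes what happens on Day 1. It does not change the gap between discharge and Day 8.

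**The case against.** The strongest reply is that footnote k is loosely worded and not meant to confine the adverse-event item to the pre-dose period. It calls for vital signs during and after the infusion, and the same column contains hypersensitivity blood assessments that can only follow a reaction. Section 12.4 leaves the item unlabelled, and Section 10.3.1 opens full reporting once the infusion has been given. This stands as far as intent goes. A rule written as mandatory still has to be reconciled with the other passages, and the reply does not touch Day 4.

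The second reply is that safeguards exist: in-clinic observation with hourly vital signs, an examination if a reaction is recognised, discharge instruction, shedding samples at 2–24 h, and continuous reporting. Nothing prevents staff from recording an event at Day 4. This too stands, and it confines the exposure to milder or delayed events after discharge. These measures rely on recognition or self-report, and none of them is scheduled questioning.

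The third is that the remedy is only partial. A pre-discharge interview covers hours already observed, and Day 4 normally falls after the window closes. That is correct: the gain is a shorter recall interval, nominally 8 − 4 = 4 days sooner.

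A reader might infer more than the documents support:
- *That infusion reactions would be lost.* The window is set by onset, so an event first reported on Day 8 still counts if it is dated correctly.
- *That the 48-hour classification is unreliable throughout.* Under footnote a, a missing hour matters only for Day 3 onsets.
- *That reaction-triggered blood samples would be taken too late.* The sampling details are redacted, so this cannot be judged.

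**Conclusion.** The point holds as a scheduling gap and a wording conflict. The protocol schedules no adverse-event questioning from discharge on infusion day until Day 8 (Days 6–10), which is 3–7 days after the SAP's window closes. Up to 40 of the 48 hours (83%) rely on self-report. The likely consequences are later site awareness and less accurate recall of mild or delayed events, with a specific loss for true 48-hour reactions on Day 3 whose hour cannot be recovered. The documents do not allow the number of such events to be estimated.

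The result rests on SAP day numbering, the stated visit windows and the minimum 8-hour stay. A longer stay shortens the unobserved period. The 21–33% range for Day 3 depends on the assumed clock times.

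A reader might take this as affecting about 40 dosed subjects. The SAP says one subject was enrolled, enrollment was terminated and only listings will be produced. The 40 is the planned number, so the point concerns the protocol as written, and its effect on this interim analysis is small.

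**What to change.** 1. In footnote k of Table 9.1.1 and in Section 12.4, state that adverse events and concomitant medications are also assessed after the infusion and before discharge. Reword footnote k so that it agrees with its own post-infusion vital signs.
2. Add the adverse-event and concomitant-medication assessment to the Day 4 column of Table 9.1.2 and to Section 12.5.2, recording onset date and time.

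The first puts a scheduled question inside the 48-hour window. The second puts one nominally a day after it closes, while a Day 3 onset hour is still likely to be remembered.

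The cost is amendment wording and two short interviews. The subject is already in the clinic on Day 1 and attending for samples on Day 4, for which the protocol gives no mobile-nursing or lab-draw-only option. No visit, procedure or staff is added. The change concerns data collection only and leaves clinical management of reactions as it is.

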**Table 9.1.2: Schedule of Events – Post-Infusion Follow-Up (Week 1-16)**

Assessment	Follow-Up After BMN 270 Infusion – Weeks*																
	Week 1		2	3	4	5 g	6	7 g	8	9 g	10	11 g	12	13 g	14	15 g	16
	D4	D8															
Study Day*	4	8	15	22	29	36	43	50	57	64	71	78	85	92	99	106	113
Physical examination a		X	X	X	X	X g	X	X g	X	X g	X						
Weight a					X				X				X				X
Assessment of Adverse Events and Concomitant Medications (including review of subject diary for bleeding and FVIII use)		X	X	X	X	X	X	X	X	X	X	X	X	X	X	X	X
Vital Signs		X	X	X	X	X g	X	X g	X	X g	X						
Blood chemistry, hematology, and coagulation tests b			X		X						X						X
Urine Tests b														X			
Liver Tests b	X	X	X	X	X	X	X	X	X	X	X	X	X	X	X	X	X
FVIII assays c		X	X	X	X	X	X	X	X	X	X	X	X	X	X	X	X
FVIII antibody titer					X				X				X				X
PCR of vector DNA in blood, saliva, urine, semen, and stools d	X	X	X	X	X		X		X			X					X
Exploratory biomarker assessments e							X					X					X
Haemo-QOL-A assessment					X							X					
EQ-5D-5L					X							X					
HAL					X							X					

Assessment	Follow-Up After BMN 270 Infusion – Weeks*																
	Week 1		2	3	4	5 g	6	7 g	8	9 g	10	11 g	12	13 g	14	15 g	16
	D4	D8															
Study Day*	4	8	15	22	29	36	43	50	57	64	71	78	85	92	99	106	113
WPAI+CIQ:HS					X								X				
PROBE					X								X				
AAV5 TAb Assay										X							X
AAV5 TI Assay										X							X
Testing for reactivation of hepatitis B and hepatitis C																	X f
PBMC collection (for determination of AAV5 and FVIII specific immunity)			X		X		X		X		X		X		X		X
VWF:Ag													X				

\* Visit windows are  $\pm$  48 hours (and include the Day 4 visit).

a Brief physical examination should be done at all weekly visits.

b Refer to [Table 9.7.8.2.1](#) for laboratory assessments to be included, and to [Table 9.7.8.3.1](#) for liver tests (LTs). LTs may be monitored more or less frequently (and in particular when ALT values are  $\geq 1.5 \times$  ULN or  $>$  ULN and  $> 2 \times$  baseline value) based on discussion between the Medical Monitor and the Investigator and review of subject data, but LTs will be monitored at least twice weekly during periods when a subject's ALT is  $\geq 3 \times$  ULN. Subjects with ALT  $\geq 1.5 \times$  ULN or  $>$  ULN and  $> 2 \times$  baseline value during the study and either an alternative etiology considered or for further evaluation of the lab abnormality may undergo additional evaluations (eg, imaging studies including MRI or ultrasound, additional blood tests, and/or liver biopsy) at the discretion of the Investigator. Additional testing of FVIII and LTs during any study week may be performed if: (1) the ALT has increased to above ULN; (2) Increases in ALT values from prior assessment are accompanied by declines in FVIII activity level; or after a discussion between the Medical Monitor and the Investigator based on a review of subject data. **If** FVIII levels and/or ALT values are stable over the course of several weeks, assessment of FVIII activity and ALT levels may be adjusted based on discussion between the Medical Monitor and the Investigator.

c Includes FVIII activity level (chromogenic substrate FVIII assay and one-stage clotting FVIII assay), Bethesda assay (with Nijmegen modification) for hFVIII inhibitor level, coagulation exploratory assay, and hFVIII protein assay. If a subject has used FVIII within 72 hours of a measurement day, all efforts should be made to obtain FVIII activity measurements when a 72-hour interval without FVIII use is achieved; the 72-hour wash-out period is only intended for subjects who have achieved FVIII  $\geq$  5 IU/dL at 16 weeks after BMN 270 infusion and who have not resumed FVIII replacement therapy. If FVIII levels are elevated or stable over the course of several weeks, assessment of FVIII activity may be adjusted based on discussion between the Medical Monitor and the Investigator. A D-dimer may be considered under circumstances in which FVIII activity levels are above the normal physiological range and/or if there is a concern for a venous thromboembolism.

d Collection for each matrix to occur until at least 3 consecutive negative results are obtained. Collection and testing of semen samples must continue at least through Week 12, even if 3 consecutive negative results in that compartment have already been recorded.

e Blood samples will be collected from subjects to evaluate biochemical, molecular, cellular, and genetic/genomic aspects relevant to hemophilia A disease, coagulation, and/or AAV gene transfer, and to develop assays used for these evaluations. Subjects may choose to opt out of the exploratory genetic/genomic research being done to study or try to discover genes that are not yet known to be associated with hemophilia A. While exploratory samples will be collected at the time points indicated above, testing of these samples (including those for TGA assay and any other exploratory assessments) will be performed only as deemed necessary by the Sponsor.

f Testing for reactivation of hepatitis B and hepatitis C at Week 16, for subjects with a past medical history of hepatitis B or hepatitis C prior to study entry, should be performed only in subjects who have not received therapeutic oral corticosteroids prior to Week 16; subjects who have received therapeutic oral corticosteroids will have hepatitis B and hepatitis C testing at the time points indicated in [Table 9.1.6](#).

g The scheduled visits at Week 5, Week 7, Week 9, Week 11, Week 13, and Week 15 may be performed by a mobile nursing (MN) professional at the subject's home or another suitable location (if the subject has given written informed consent to participate in MN visits), or at the site as a shortened lab draw-only visit. The MN service or site will collect blood samples at these visits. For site lab draw-only visits, sites will contact the subject via phone call or e-mail to collect information regarding adverse events, changes to concomitant medications, bleeding episodes, and FVIII use. For MN visits, the service will collect this information. The physical examination and vital signs assessments listed in the Schedule of Events will not be performed at these MN or lab draw-only visits.

Table 9.1.3: Schedule of Events – Post-Infusion Follow-Up (Week 17-32)

Assessment	Follow-Up After BMN 270 Infusion – Weeks*															
	17 f	18	19 f	20	21 f	22	23 f	24	25 f	26	27 f	28	29 f	30 f	31 f	32
Study Day*	120	127	134	141	148	155	162	169	176	183	190	197	204	211	218	225
Physical examination a	X f	X	X f	X	X f	X	X f	X	X f	X	X f	X	X f	X f	X f	X
Weight a				X				X				X				X
Assessment of Adverse Events and Concomitant Medications (including review of subject diary for bleeding and FVIII use)	X	X	X	X	X	X	X	X	X	X	X	X	X	X	X	X
Vital Signs	X f	X	X f	X	X f	X	X f	X	X f	X	X f	X	X f	X f	X f	X
Blood chemistry, hematology, and coagulation tests b						X				X						X
Urine Tests b										X						
Liver Tests b	X	X	X	X	X	X	X	X	X	X	X	X	X	X	X	X
FVIII assays c	X	X	X	X	X	X	X	X	X	X	X	X	X	X	X	X
FVIII antibody titer				X				X		X						X
PCR of vector DNA in blood, saliva, urine, semen, and stools d				X				X		X						X
Exploratory biomarker assessments e				X				X		X						X
Haemo-QOL-A assessment										X						
EQ-5D-5L										X						

Assessment	Follow-Up After BMN 270 Infusion – Weeks*															
	17 f	18	19 f	20	21 f	22	23 f	24	25 f	26	27 f	28	29 f	30 f	31 f	32
Study Day*	120	127	134	141	148	155	162	169	176	183	190	197	204	211	218	225
HAL										X						
WPAI+CIQ:HS										X						
PROBE										X						
AAV5 TAb Assay								X							X	
AAV5 TI Assay							X								X	
PBMC collection (for determination of AAV5 and FVIII specific cellular immunity)		X		X		X		X		X		X			X	
VWF:Ag										X						
TGA Assay e				X				X		X					X	

\* Visit windows are  $\pm$  48 hours.

a Brief physical examination should be done at all weekly visits except Week 26, where a complete physical examination should be performed. Weight should be recorded at Week 20 and every 4 weeks.

b Refer to [Table 9.7.8.2.1](#) for laboratory assessments to be included, and to [Table 9.7.8.3.1](#) for liver tests. LTs may be monitored more or less frequently (and in particular when ALT values are  $\geq 1.5 \times$  ULN or  $>$  ULN and  $> 2 \times$  baseline value) based on discussion between the Medical Monitor and the Investigator and review of subject data, but LTs will be monitored at least twice weekly during periods when a subject's ALT is  $\geq 3 \times$  ULN. Subjects with ALT  $\geq 1.5 \times$  ULN or  $>$  ULN and  $> 2 \times$  baseline value during the study and either an alternative etiology considered or for further evaluation of the lab abnormality may undergo additional evaluations (eg, imaging studies including MRI or ultrasound, additional blood tests, and/or liver biopsy) at the discretion of the Investigator. Additional testing of FVIII and LTs during any study week may be performed if: (1) the ALT has increased to above ULN; (2) Increases in ALT values from prior assessment are accompanied by declines in FVIII activity level; or after a discussion between the Medical Monitor and the Investigator based on a review of subject data. If FVIII levels and/or ALT values are stable over the course of several weeks, assessment of FVIII activity and ALT levels may be adjusted based on discussion between the Medical Monitor and the Investigator.

c Includes FVIII activity level (chromogenic substrate FVIII assay and one-stage clotting FVIII assay), Bethesda assay (with Nijmegen modification) for hFVIII inhibitor level, coagulation exploratory assay, and hFVIII protein. If a subject has used FVIII within 72 hours of a measurement day, all efforts should be made to obtain FVIII activity measurements when a 72-hour interval without FVIII use is achieved; the 72-hour wash-out period is only intended for subjects who have achieved FVIII  $\geq 5$  IU/dL at 16 weeks after BMN 270 infusion and who have not resumed FVIII replacement therapy. If FVIII levels are elevated or stable over the course of several weeks, assessment of FVIII activity may be adjusted based on discussion between

the Medical Monitor and the Investigator. A D-dimer may be considered under circumstances in which FVIII activity levels are above the normal physiological range and/or if there is a concern for a venous thromboembolism.

dCollection for each matrix to occur until at least 3 consecutive negative results are obtained.

eBlood samples will be collected from subjects to evaluate biochemical, molecular, cellular, and genetic/genomic aspects relevant to hemophilia A disease, coagulation, and/or AAV gene transfer, and to develop assays used for these evaluations. Subjects may choose to opt out of the exploratory genetic/genomic research being done to study or try to discover genes that are not yet known to be associated with hemophilia A. While exploratory samples will be collected at the time points indicated above, testing of these samples (including those for TGA assay any other exploratory assessments) will be performed only as deemed necessary by the Sponsor.

fThe scheduled visits at Week 17, Week 19, Week 21, Week 23, Week 25, Week 27, Week 29, Week 30, and Week 31 may be performed by a mobile nursing (MN) professional at the subject's home or another suitable location (if the subject has given written informed consent to participate in MN visits), or at the site as a shortened lab draw-only visit. The MN service or site will collect blood samples at these visits. For site lab draw-only visits, sites will contact the subject via phone call or e-mail to collect information regarding adverse events, changes to concomitant medications, bleeding episodes, and FVIII use. For MN visits, the service will collect this information. The physical examination and vital signs assessments listed in the Schedule of Events will not be performed at these MN or lab draw-only visits.

